In Aim 3, identifying intervention-related resources and the comprehensive economic evaluation will be led by [name] (Sub-contract PI) with guidance from [name] (Co-I). Specifically, the Cornell team will ensure that site-specific information is collected to inform the tailored microcosting questionnaire for the trial; control for potentially confounding factors in multivariable regressions and identify relevant factors for sensitivity analyses; tailor statistical methods to accommodate site heterogeneity; appropriate price weights for resources required to implement and continually manage each strategy; and conduct a comprehensive economic evaluation of the intervention.

Each site and collaborating investigators/study teams will be responsible for all study procedures, including but not limited to: recruitment, consent, data collection, and data storage and shipment. WCG will be the IRB of Record for the study and therefore will submit all protocol documentation for review and approval and will be responsible for reporting any updates and/or events that occur throughout the study procedures. Data will be collected and stored at both sites (NKI and FRI) with FRI periodically sending the data to NKI. Any process measures pertaining to the text messaging tool will be collected and stored at FRI in partnership with the HIPAA compliant texting vendor, QligSOFT.

Study Synopsis

Black and Latinx people who use opioids (PWUO) bear a disproportionate burden of opioid overdose deaths. The economic burden faced by Black and Latinx PWUO has also risen due to costs associated with excess mortality and utilization of high-cost healthcare services. Compared to White PWUO, Black and Latinx PWUO are less likely to be initiated on buprenorphine in emergency department (ED) settings and establish care in primary care for the treatment of opioid use disorder (OUD). Racial disparities among PWUO in primary care are driven by social determinants of health (SDH; e.g., lack of peer support or health insurance) and may be partially addressed by adopting innovative *mobile health* and *peer coaching* strategies.

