To achieve Aim 1, potential study participants with opioid use disorder (OUD) will be identified and recruited in the hospital emergency department (ED) and community settings. The study team has over two decades of experience enrolling and tracking patient participants in these high-risk communities. Each of these cohorts includes people who use opioids who are *not prescribed* any medication for opioid use disorder (MOUD), including methadone or buprenorphine, in the 30 days preceding their study enrollment.

Study settings

Planned study sites for participant enrollment will include NYC Health+Hospitals affiliated hospitals (e.g., Lincoln Hospital), the START Treatment and Recovery centers, and community settings associated with high rates of opioid overdose deaths among Black and Latinx adults in New York City.

The **study sample** of 252 Black and Latinx PWUO with a positive urine toxicology result per the Hospital EMR will be identified by the study team and approached in the ED or in community settings among PWUO self-reporting OUD and confirmed with random saliva toxicology testing and recruited over a 2-year period and followed for a duration of 12-months with purposeful recruitment of male: female adults along a 2:1 target ratio (169 males: 83 females) and a target minimum 25% aged 18-29 (see *Figure 1*). We will use venue-based and street outreach in spaces where opioid-related overdose rates are highest, and in neighborhoods where harm reduction services are located.

Potential study participants will be informed of study details by the study team, undergo informed consent, complete baseline REDCap assessment, and will then be randomized (1:1:1) using a random block design (block sizes 3, 6, 9) to 1 of 3 study arms, stratified by gender. Finally, participants will be compensated for their time at visit end and given an appointment schedule for in-person or remote survey visits. Randomly selected participants from intervention arm 1 (n=30) will be invited for the qualitative implementation interviews (see Aim 2). All randomized participants who need a phone will be provided one by the study and tracked over

time by leveraging Drs. [name]', [name]'s, and [name]'s study tracking and retention expertise in the event of changes to mobile phone numbers.

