The sample size, N=252, was chosen to provide sufficient power for analyses associated with the defined primary outcomes and accounting for 20% attrition. In the absence of normative data, based on results of prior studies among emergency department enrolled PWUO that indicate modest uptake of MOUD (~5%¹⁹¹), and completing referrals to MOUD services (~25%¹⁹²⁻¹⁹⁴), we compute the power to detect significant effects. Using these estimates as the baseline, we anticipate that interactive texting will increase completing referrals to primary care from 25% to 35% ¹⁹⁵⁻¹⁹⁷. The combination of interactive texting and PRC support will enhance time to completing referrals to primary care from 25% to 45%. These anticipated changes indicate odds ratios for intervention versus TAU (effect size) of between 1.5 to 2.0 for OUD-related outcomes. We use these estimated odds ratios (ORs) as the proxy for the rate in treatment versus the control. Evidence from methodological studies assert a useful equivalence involving the hazard ratio (HR), such that when the PH assumption is reasonable, the HR is equivalent to the odds that a randomly chosen person with hazard represented in the numerator will experience the event of interest before a randomly chosen person with hazard represented in the denominator 198-200. The power to detect these effects with α =0.05 (two-tailed) using log-rank comparisons for survival outcomes via the power procedure in SAS v9.4 is ~80%.

Enrollment, Consent and Workflow

Over a 2-year period, Black / Latinx PWUO (N=252) identified in the ED or community by the study team using the electronic medical records (EMR) or self-report will be screened and enrolled by the study team. Specifically, ED-recruited Black and Latinx PWUOs with a positive urine toxicology per the Hospital EMR or self-reporting illicit opioid use among PWUO approached in community settings and confirmed with random saliva toxicology testing will be enrolled over a 2-year period. Community-recruited PWUO participants will complete enrollment in the in private conference rooms located in Lincoln Hospital or START Treatment and Recovery centers or in the NYS OMH Harlem field office site. Given the ethical importance to expand enrollment of vulnerable and hard-to-reach persons living with substance use, including women, unstably housed, and uninsured adults, we will provide reimbursement for peer-driven recruitment (\$25, max 3 referrals per participant).

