Participants randomized to TAU will receive similar payments at the same time points as participants in the intervention arm-1 and arm-2 groups. At the completion of each of the follow-up sessions all participants are compensated for their time.

Proposed Analyses

Aim 1 is a 3-year RCT involving community and ED-enrolled Black / Latinx PWUO who will be screened and enrolled (N=252) **Primary outcomes** will be based on remote and/or in-person follow-up assessments at 3-, 6-, and 12-months and consists of self-reported linkage to primary care-based OUD services (i.e., time to initial receipt of buprenorphine in primary care). **Secondary outcomes** include durability of treatment effect at 52 weeks (e.g., continuous retention in OBOT with buprenorphine), receipt of social services, and longitudinal engagement with the proposed intervention (up to 26 weeks).

Our primary hypothesis is that the rate of linkage to OBOT, i.e., time to first buprenorphine prescription, will be highest among PWUO participants randomized to texting + PRC, followed by those randomized to texting only, then to TAU. To assess this hypothesis, we will utilize Cox proportional hazards (PH) regression to investigate differences in time to service linkage (in days) by intervention group. Cox PH regression is a method for investigating the effect of several variables on the time to a specified event¹⁷⁰. Cumulative hazards functions for the intervention groups will be examined using Nelson-Aalen plots and use the supremum test which uses martingale residuals to check the proportional hazards assumption. If the assumption is violated such that there is no difference in the direction of the association but there is variation in the magnitude of the association, i.e., the hazards ratio (HR) changes over time, then the coefficient that we estimate for that covariate is akin to an 'average effect' over timepoints that are observed in a dataset and the Cox PH model will perform moderately. If the hazards cross, i.e., a change in the direction of the association, the Cox PH model will perform poorly, and we will extend the Cox model to allow for nonproportional hazards using time dependent covariates. Intervention group as assigned will be the sole explanatory variable in the models (see **Methodological Considerations and Alternatives**).

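### Recruitment source (ED or community) is in neither the randomization nor the primary Cox model; stratifying the Aim 1 analysis by source is a cheap efficiency gain

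*Combined protocol and SAP*

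**What the plan says.** **Sources.** Under Study settings (Study Design, Aim 1), the protocol states: "Planned study sites for participant enrollment will include NYC Health+Hospitals affiliated hospitals (e.g., Lincoln Hospital), the START Treatment and Recovery centers, and community settings". It adds: "We will use venue-based and street outreach in spaces where opioid-related overdose rates are highest". Under Enrollment, Consent and Workflow it adds paid peer referral: "we will provide reimbursement for peer-driven recruitment". One sentence under Study Strategy describes all 252 as screened in the ED, but the workflow chart, the Aim 1 design, the enrolment section and the Recruitment section all describe both ED and community routes.

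**Entry.** ED recruits qualify through a positive urine toxicology in the hospital record. Community recruits qualify through self-report confirmed by a saliva test (Study settings; Inclusion/Exclusion criteria, item 7).

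**Randomization.** Under Study settings, participants "will then be randomized (1:1:1) using a random block design (block sizes 3, 6, 9) to 1 of 3 study arms, stratified by gender". Wherever allocation is described, gender is the only stratification factor.

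**Primary analysis.** Under Proposed Analyses, "we will utilize Cox proportional hazards (PH) regression to investigate differences in time to service linkage (in days) by intervention group". The same paragraph ends: "Intervention group as assigned will be the sole explanatory variable in the models", with a pointer to Methodological Considerations and Alternatives. That paragraph, and Data Entry & Analysis, add variables found to be imbalanced at baseline. The variables listed for comparison do not include recruitment source.

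**Planning rates.** The Cohort section takes its baseline rates from studies of ED-enrolled people. No rate is given for community recruits, and none by source.

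**The concern.** A person leaving an ED and a person met through street outreach or a peer may have different underlying rates of a first buprenorphine prescription. If so, source is prognostic, and a Cox model or log-rank test that ignores it mixes two baseline hazards. In time-to-event models this pulls the unadjusted hazard ratio somewhat toward 1 relative to the within-source ratio. It costs power even when the arms are perfectly balanced on source. A rule triggered by observed imbalance cannot recover that loss. The rule also depends on the data and sits awkwardly beside the statement that arm is the only explanatory variable. What is at stake is efficiency in a trial with little to spare.

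**Working it through.** **1. The plan's own figure.** Inputs from the Cohort section: linkage 25% under TAU and 45% under texting plus peer coach, 84 per arm, two-sided α = 0.05.

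- HR for exponential times = ln(1 − 0.45) / ln(1 − 0.25) = 0.598 / 0.288 = 2.08.
- Events = 84 × (0.25 + 0.45) = 58.8.
- Schoenfeld power = Φ(½ · √58.8 · ln 2.08 − 1.96) = Φ(0.84) = 80.1%.

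So about 80% is reproduced for the largest contrast with no attrition. With 20% removed (67.2 per arm, 47 events) it is 70.8%. That shortfall is a separate matter and has nothing to do with source.

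**2. Adding a source effect.** The source hazard ratios are assumptions, because the documents supply none. The check simulated 20,000 trials per scenario: arm 1 versus TAU, 84 per arm, two equally sized sources, exponential times censored at 12 months, TAU linkage 25% overall, gender-only randomization. The unadjusted log-rank test (equivalent to Cox with arm only) was compared with the log-rank test stratified by source. Monte Carlo error is about √(0.78 × 0.22 / 20,000) = 0.3 points per power figure.

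Treatment HR fixed at 2.08 within each source, no attrition:

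| Source HR | TAU linkage by source | Unadjusted | Stratified |
|---|---|---|---|
| 1 | 25% / 25% | 78.9% | 78.5% |
| 1.5 | 21% / 29% | 78.3% | 78.5% |
| 2 | 18% / 32% | 76.6% | 78.4% |
| 3 | 14% / 36% | 73.6% | 77.6% |
| 4 | 12% / 39% | 71.4% | 77.8% |

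The changes are about 0, 0, +2, +4 and +6 points. With 20% uniform dropout they are nearly the same (source HR 4: 67.1% to 73.2%).

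**3. Holding the planned rates instead.** Fixing the HR at 2.08 within source lowers the overall arm-1 rate. At source HR 4 (TAU 11.5% and 38.5%), the arm-1 rates are 1 − 0.885^2.08 = 22.4% and 1 − 0.615^2.08 = 63.6%, an average of 43.0% rather than 45%. If 25% versus 45% is held overall, the within-source HR at source HR 4 becomes 2.23, and power is 79.4% unadjusted and 85.5% stratified. With 20% uniform dropout:

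| Source HR | Unadjusted | Stratified |
|---|---|---|
| 1 | 73.9% | 73.5% |
| 2 | 74.7% | 76.4% |
| 3 | 76.0% | 80.1% |
| 4 | 75.9% | 82.3% |

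The gain from stratifying is the same, but unadjusted power does not fall as the sources diverge.

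**4. Validity and randomization.** With no treatment effect and gender-only randomization, the unadjusted test rejects in 4.8% (source HR 2) and 5.0% (source HR 4) of trials. Stratifying the randomization by source, without changing the analysis, adds about 0 to 2 points of power and makes the unadjusted test slightly conservative (4.1% at source HR 4).

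**The case against.** **Sources may differ little.** Everyone must have DSM-5 OUD, an opioid-positive test and a stated interest in starting buprenorphine, and nobody may have been prescribed MOUD in the previous 30 days. These criteria narrow the difference, and at a source HR of 1.5 the gain is negligible. This stands, and it is why the point is modest. Stratifying costs essentially nothing in that case.

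**The plan already allows adjustment.** The imbalance rule could bring source in. It does not name source, however, and it addresses imbalance rather than the efficiency lost when arms are balanced.

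**Power is not shown to fall below plan.** A reader might infer that the stated 80% assumes a homogeneous population and is therefore wrong. Step 3 shows otherwise: if 25% and 45% are the overall rates, unadjusted power stays where it was, and stratifying adds power above plan. A reader might also point to TAU linkage of 10%/42% or 5%/45% by source, where unadjusted power is about 68% or 60%. Those pairs imply source hazard ratios of ln 0.58 / ln 0.90 = 5.2 and ln 0.55 / ln 0.95 = 11.7, and arm-1 rates of 43.7% and 40.6%, below the planned 45%. With 45% held, unadjusted power is about 76% and 81%. They are extremes that nothing in the documents supports.

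**Site heterogeneity in Aim 3.** The undertaking to "tailor statistical methods to accommodate site heterogeneity" belongs to the economic analysis and concerns sites. It is not evidence that recruitment route matters for linkage.

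**A finer split is not supported.** START is listed as an enrolment site, but community recruits may complete enrolment at Lincoln Hospital, START or the Harlem office, so place of enrolment is not source. The screening log lists gender, race/ethnicity and opioid type only.

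**Conclusion.** The point holds as a cheap improvement in efficiency. Source is absent from both the randomization and the primary model, and the imbalance rule does not fill the gap. The gain for arm 1 versus TAU is about 0, 2, 4 and 6 points of power at source hazard ratios of 1, 2, 3 and 4. This rests on two equal sources, exponential times and the same treatment hazard ratio in each source. The true size cannot be computed from the documents. Chance imbalance in source mix may occur, but a reader should not infer bias or an inflated type I error from it, since the error rate stays at its nominal level. Nor does the point overturn the stated power.

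**What to change.** Before outcomes are examined by arm, amend the Aim 1 paragraph under Proposed Analyses, and the matching text under Data Entry & Analysis. State that the primary Cox model has arm as its explanatory variable and is stratified by recruitment source (ED or community), with a log-rank test stratified in the same way. Report the hazard ratio by source descriptively. Define source by where the person was first approached, state how peer-referred people are classed, and record it as an explicit enrolment field. For people already enrolled, ED versus community may be recoverable from the toxicology route.

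The cost is one field, a short amendment, and a hazard ratio that is conditional on source. It will differ somewhat from the marginal ratio: in step 3, 2.23 within source against 2.08 for the same overall 25% and 45%. Changing the randomization is not needed, because nearly all the gain comes from the analysis.

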Primary outcomes: Participants, regardless of study arm, will complete remote and/or in-person follow-up assessments at 3-, 6-, and 12-months. *The primary outcome for this efficacy study* is self-reported linkage to OUD services (i.e., time to initial buprenorphine prescription that is prescribed in OBOT programs or other OUD treatment providers per the Non-study Medical and Other Services form.

Secondary outcomes include durability of treatment effect at 52 weeks (e.g., continuous retention in OBOT with buprenorphine), receipt of social services, and longitudinal engagement with the proposed intervention (up to 26 weeks)

Aim 2 will evaluate the implementation of the multimodal intervention (arm-2) at 3-, 6-, and 12-months using RE-AIM and CFIR linked to a public hospital setting offering OBOT with buprenorphine. In-depth interviews with frontline providers (n=10), administrators (n=10), and a subset of PWUO participants from intervention arm-2 (n=30) will be interviewed to contextualize patient-, provider-, and systems-level factors influencing intervention delivery.

Aim 3 will identify resources and cost estimates required to implement and sustain the multimodal intervention, incorporate these costs into a customizable budget-impact tool (Aim 3a), and conduct a rigorous economic evaluation to calculate the relative economic value of each arm (incremental cost / QALY) from the healthcare, state-policymaker, and societal perspectives (Aim 3b).

Successfully harnessing mHealth tools to address primary care clinical outcomes (Aim 1)

Over the last decade, our team has refined mHealth strategies to address disparities in primary care. Our initial findings demonstrated that the adoption of telephone encounters among Bellevue primary care providers during Hurricane Sandy in 2012 were not associated with any increases in missed appointments (p=0.52) or illicit opioid reuse (p=0.66) at 6 months (N=132)^{125,126}. In 2020, our team co-founded the city-wide NYC H+H telemedicine program that provides same-day prescribing of buprenorphine and naloxone (N=199)^{35,42,106}. These findings demonstrated that the adoption of a multimodal mobile health strategy offers an innovative risk mitigation strategy to minimize the impact of disasters on primary care engagement among PWUO.

Can the multimodal intervention be equitably implemented in clinical care? (Aim 2)

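### The ~80% power rests on rates of completing a referral, not on the analysed event (first buprenorphine prescription), for which no treatment-as-usual (TAU) rate is given

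*Combined protocol and SAP*

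**What the plan says.** **Endpoint.** Study Strategy (Primary outcomes) defines the primary outcome as "time to initial buprenorphine prescription that is prescribed in OBOT programs or other OUD treatment providers". Proposed Analyses words it as "time to initial receipt of buprenorphine in primary care", and states the primary hypothesis as "the rate of linkage to OBOT, i.e., time to first buprenorphine prescription, will be highest among PWUO participants randomized to texting + PRC". The two definitions differ on where the prescription may come from. Both make the event a buprenorphine prescription or its receipt.

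**Sample size.** Study Design, Cohort says that N=252 powers the defined primary outcomes with 20% attrition allowed for. It cites two background rates from prior studies of "emergency department enrolled PWUO that indicate modest uptake of MOUD": about 5% for that uptake, and about 25% for completing referrals to MOUD services. The effects that follow all concern referrals. For texting alone, "we anticipate that interactive texting will increase completing referrals to primary care from 25% to 35" per cent. For texting plus peer support, the plan expects to "enhance time to completing referrals to primary care from 25% to 45" per cent. These are summarised as odds ratios of 1.5 to 2.0, taken as proxies for the HR, with ~80% power for two-sided log-rank comparisons at 0.05.

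The 5% figure enters no stated effect. The sample-size text repeated under Proposed Analyses lists both background rates again and takes them no further.

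**The concern.** Log-rank power depends on the number of events. The plan counts expected events from one quantity (a completed referral) and will analyse another (a first prescription). The OBOT programmes start eligible patients on buprenorphine (Enrollment, Consent and Workflow), so someone can complete a referral without receiving a prescription. If prescriptions are rarer than completed referrals, the trial will have fewer events than planned. A null result could then not be told apart from a shortage of events, and the ~80% would be quoted for an endpoint it was not computed for.

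**Working it through.** **Inputs.** Two-sided alpha 0.05, log-rank test, 1:1:1 allocation, 252/3 = 84 per arm, and 84 × 0.8 = 67.2 after the stated 20% attrition. Referral rates are 25%, 35% and 45%, and the stated ratio range is 1.5 to 2.0 (all from Cohort and Study Procedures). Participants lost still contribute some follow-up, so 84 and 67.2 bracket the effect of a 20% loss.

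**Formulas.** HR = ln(1−p₁)/ln(1−p₀). Events d = n(p₀+p₁) for n per arm. Schoenfeld power = Φ(|ln HR|·√(d/4) − 1.96).

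**Step 1: the plan's own figure, with the referral rates at face value.**
- 25% vs 45%: HR = ln 0.55/ln 0.75 = 2.08 and d = 84 × 0.70 = 58.8. Power = Φ(0.7315 × 3.834 − 1.96) = Φ(0.845) = **80%**. At 67.2 per arm, d = 47.0 and power is **71%**.
- 25% vs 35%: HR = 1.50 and d = 50.4. Power is **30%**; at 67.2 per arm, **25%**.

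On the rates and test as stated, ~80% is therefore reached only for texting plus peer support vs TAU with attrition ignored. A three-group, 2-df log-rank test gives 71% (61% after attrition). The odds ratio implied by 25% vs 45% is 2.45. Treated as an HR it would give 93% (87%), but it lies outside the plan's stated 1.5 to 2.0 and disagrees with the HR of 2.08 that the same rates imply.

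**Step 2: vary the TAU rate and hold the HR constant.** Here p₁ = 1 − (1−p₀)^HR. Example at TAU 5%, HR 2.0: p₁ = 1 − 0.95² = 0.0975, d = 84 × 0.1475 = 12.4, power = Φ(0.693 × 1.760 − 1.96) = Φ(−0.740) = 23%.

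| TAU rate | Events, HR 2.0, 84/arm | Power, HR 2.0: 84 / 67.2 per arm | Power, HR 1.5: 84 / 67.2 per arm |
|---|---|---|---|
| 5% | 12.4 | 23% / 19% | 10% / 8.5% |
| 10% | 24.4 | 40% / 33% | 15% / 13% |
| 15% | 35.9 | 55% / 46% | 20% / 17% |
| 20% | 47.0 | 66% / 57% | 25% / 21% |
| 25% | 57.8 | 75% / 65% | 30% / 25% |

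For 80% power the same formula needs 66 events at HR 2.0 and 191 at HR 1.5. No cell reaches 80%.

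**Step 3: vary the TAU rate and hold the absolute gain constant.**

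| TAU rate | +20 points: HR; power 84 / 67.2 | +10 points: HR; power 84 / 67.2 |
|---|---|---|
| 5% | 5.61; 99% / 97% | 3.17; 66% / 56% |
| 10% | 3.39; 94% / 89% | 2.12; 47% / 39% |

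On this scale power rises as the TAU rate falls, the reverse of Step 2.

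**The case against.** The strongest reply is that the protocol treats linkage and prescription as one event, since it defines linkage by the first prescription, and that completing a referral to MOUD services is a reasonable proxy for that. This stands in part. The documents do not show that the two rates differ fivefold. Nor do they state or justify the proxy, and they cite a separate, much lower rate for medication uptake in the same sentence.

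A reader might infer that the true TAU rate is about 5% and that power is therefore about 20%. The documents do not support that. The 5% covers all MOUD in emergency department cohorts, with no time horizon given, and its reference number leads in the reference list to a paper on checking the Cox model, so it cannot be traced. This trial also recruits in the community, requires interest in starting buprenorphine (inclusion criterion 9), gives control participants service referrals at each survey visit, and follows people for 12 months. Most of this points to a rate above 5%.

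A reader might also infer that a lower TAU rate must cost power. That depends on the effect scale. The plan states its effects first as absolute changes and then converts them to ratios. Step 3 shows that a preserved 20-point gain would raise power. The HRs this requires, 5.6 at TAU 5% and 3.4 at 10%, lie well outside the plan's 1.5 to 2.0, so a sponsor relying on it would have to say so and defend it.

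**Conclusion.** The concern holds as a mismatch between the power calculation and the endpoint. The ~80% is computed for completing a referral, and the plan gives no TAU rate for the event it will analyse. The size of any shortfall is conditional. With a constant HR of 2.0 and a TAU rate between 5% and 25% (an assumed range whose ends are the plan's two cited rates), power is 23% to 75% at 84 per arm and 19% to 65% after 20% attrition. At HR 1.5 it is 10% to 30% and 8.5% to 25%. Within the plan's own ratio range, no TAU rate in that span reaches 80%. With a constant 20-point gain, power at the low TAU rates would instead be adequate.

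Part of the gap is unrelated to the endpoint. At the 25% referral rate, texting plus peer support falls to 71% once the stated attrition is applied, and texting only has 30% (25% after attrition). A single ~80% does not describe both comparisons.

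**What to change.** In Cohort, and in the sample-size text repeated under Proposed Analyses:
- State and justify the assumed 12-month TAU rate for first buprenorphine prescription, under one settled definition of where it may be prescribed. If completing a referral is meant as a proxy, say so and support it.
- Declare whether the effect is assumed constant as an HR or as an absolute difference.
- Replace the single ~80% with expected events and power for each comparison, after 20% attrition, over a range of TAU rates such as 5% to 25%.

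This is a change of wording plus a short table. It does not touch eligibility, treatment or alpha. The cost is that the stated power becomes less favourable, most clearly for texting only.

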The primary aim of this proposal is thus to determine whether a multimodal intervention that combines artificial intelligence (AI)-driven texting that delivers cultural and social determinants of health (CSDH)-focused content prioritizing access to social services to enhance receipt of OUD services (3-5 texts/daily) in primary care among PWUO combined with peer recovery coach (PRC)-supported text-based care/services coordination that ensures real-time responses for unanticipated social, administrative, and clinical issues to enhance receipt of social services and OUD services (3-4 texts/weekly) can improve receipt of buprenorphine in primary care. j

Study Strategy

The proposed three-arm comparative effectiveness trial will evaluate the efficacy of a multimodal intervention among community and ED-enrolled Black / Latinx PWUO that combines: 1) Artificial intelligence (AI)-driven texting that delivers cultural and social determinants of health (CSDH)-focused content prioritizing access to social services to enhance receipt of buprenorphine (3-5 texts/daily) in primary care among PWUO (intervention arm-2); 2) Peer recovery coach (PRC)-supported text-based care/services coordination that ensures real-time responses for unanticipated social, administrative, and clinical issues to enhance receipt of social services and buprenorphine in primary care (3-4 texts/weekly); and 3) employing a novel and evidence-supported Cultural & Structural Humility (CSH) training for PRCs that attends to the cultural and social determinants (CSDH) including contending with intersectional stigma and discrimination through empowerment/advocacy, health habitus insights, and patient navigation (intervention arm-1).

Aim 1 will entail 252 Black / Latinx PWUO screened in the hospital ED and randomized to Aldriven CSDH-enhanced texting + PRC-supported text-based care/services coordination (*intervention arm-1*) vs. Al-driven CSDH-enhanced texting only (*intervention arm-2*) vs. TAU (*control*) defined as receipt of printed social/primary care services referrals. Intervention activities will span 26 weeks and data collection will include in-person or virtual REDCap surveys at baseline-, 3-, 6-, and 12-months, and in-depth interviews following survey period to assess fidelity, implementation, and characterization of intervention efficacy.

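### The single ~80% power figure does not hold for texting only versus TAU (25% to 35%): about 30–62% with no loss, depending on a time point the plan does not state

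*Combined protocol and SAP*

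**What the plan says.** The Cohort section says that N=252 "was chosen to provide sufficient power for analyses associated with the defined primary outcomes and accounting for 20% attrition". It starts from a 25% baseline for completed referrals and then gives two effects:

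- texting only: "we anticipate that interactive texting will increase completing referrals to primary care from 25% to 35" per cent;
- texting plus peer recovery coach (PRC): "The combination of interactive texting and PRC support will enhance time to completing referrals to primary care from 25% to 45" per cent.

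It summarises them this way: "These anticipated changes indicate odds ratios for intervention versus TAU (effect size) of between 1.5 to 2.0 for OUD-related outcomes". It then converts them to a survival effect: "We use these estimated odds ratios (ORs) as the proxy for the rate in treatment versus the control". One power closes the paragraph, at two-sided alpha 0.05: "using log-rank comparisons for survival outcomes via the power procedure in SAS v9.4 is ~80" per cent.

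No time point is attached to the 25%, 35% and 45%, and there is no event count, power per comparison or attrition calculation. The Aim 1 text under Proposed Analyses repeats N and the 20% without adding these. On timing, Study Strategy says "Intervention activities will span 26 weeks", and Study settings has participants "recruited over a 2-year period and followed for a duration of 12-months". The primary hypothesis under Proposed Analyses orders all three arms, so texting only versus TAU is part of it.

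**The concern.** The two effects differ greatly in size: a 10-point and a 20-point difference from the same control rate, with the same number per arm. One power figure can hardly describe both. The smaller effect is the one a reader needs in order to judge texting without a coach, which is presumably the cheaper option.

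If texting alone truly raises linkage from 25% to 35%, the design misses it about 38–70% of the time with no loss, and about 47–75% of the time if 20% of participants contribute no follow-up. Someone told that power is ~80% for these effects could take a non-significant texting-only result as evidence of no effect.

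**Working it through.** **Inputs.** From Cohort: control 25%, texting only 35%, texting plus PRC 45%; two-sided 0.05; log-rank; 20% attrition. From the arm descriptions: 84 per arm, so 67 after 20% loss (84 × 0.8 = 67.2). From Study settings: 12 months of follow-up. The time point of the rates is not stated, so I assume each visit time in turn (12, 6 and 3 months) and extend to month 12 with a constant hazard.

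**Formulas.** HR = ln(1−p₁)/ln(1−p₀). Events for 80% power (Schoenfeld, 1:1) = 4(1.960+0.842)²/(ln HR)². Power = Φ(√events × |ln HR|/2 − 1.960).

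**1. Implied effects.**
- 25% to 35%: HR = ln 0.65/ln 0.75 = 1.497; OR = (0.35/0.65)/(0.25/0.75) = 1.62.
- 25% to 45%: HR = ln 0.55/ln 0.75 = 2.078; OR = (0.45/0.55)/(0.25/0.75) = 2.45.

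The stated OR range is 1.5 to 2.0, so the second OR lies outside it.

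**2. Reproducing ~80%.** Texting plus PRC versus TAU, 12-month rates, 84 per arm, no loss: events = 84 × (0.25+0.45) = 58.8, power 80.1%. With 67 per arm: 46.9 events, 71%. Under this reading the figure matches the larger effect with no attrition allowance.

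**3. Limit for texting only versus TAU that needs no time point.** At HR 1.5 (the low end of the stated range), 80% power needs 191 events; at 1.497 it needs 193. The two arms hold 168 people. If all 168 linked, power would be 74–75%; if all 134 remaining after 20% loss linked, 65%.

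**4. Power at the visit times** (84 per arm with no loss / 67 per arm).

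| Rates taken at | 12-month rates: TAU, texting, texting+PRC | Texting vs TAU | Texting+PRC vs TAU |
|---|---|---|---|
| 12 months | 25%, 35%, 45% | 30% / 25% | 80% / 71% |
| 6 months | 44%, 58%, 70% | 46% / 38% | 95% / 89% |
| 3 months | 68%, 82%, 91% | 62% / 53% | 99% / 97% |

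Log-rank simulation at 84 per arm agrees: 29%, 46% and 62% for texting only; 79%, 95% and 99% for texting plus PRC.

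**5. The plan's own proxy, OR used as HR.** For texting only, with 1.62 as the HR, power is 41%, 61% and 78% (12-, 6-, 3-month rates) at 84 per arm, and 34%, 52% and 68% at 67. Eighty per cent needs 136.5 events. With no loss that means about 74% of TAU linked by month 12 (25% by about 2.6 months). At 67 per arm the ceiling is 79% even if everyone links. For texting plus PRC with 2.45 as the HR and 12-month rates, power is 93–95% at 84 and 87–89% at 67, depending on how events are counted. With the HR set to 2.0, the top of the stated range, and TAU at 25% by month 12, power is 75% / 65%.

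**6. Attrition.** Subject Payment projects 155 of 252 at month 12 and Projected attrition rates projects 153: losses of 1−155/252 = 38.5% and 1−153/252 = 39.3%, against 20% in the sample-size text. Applying the second table and censoring at the last visit, texting only versus TAU has 22% (12-month rates) or 34% (6-month rates), and texting plus PRC versus TAU 64% or 85%.

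**The case against.** The strongest reply is that the ~80% may not be a pairwise claim. The text says log-rank comparisons without naming contrasts, and the hypothesis is ordered. A three-arm trend test with 12-month rates and 84 per arm has about 79% power. With 6-month rates and 67 per arm, a three-group log-rank has about 82%, and the two texting arms combined versus TAU about 79%. So a figure near 80%, even after 20% loss, can be obtained from these rates. But the plan names none of these tests, and none isolates the texting-only effect. What stands is that the defect may be partly an unnamed test, and the fix allows for that.

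Second, three months is not a true upper limit. If 25% and 35% were 2-month rates, texting only versus TAU would have 69% (HR 1.497) or 83% (OR as HR) with no loss; for 1-month rates, 74% or 87%. That is correct. The proxy can pass 80%, but only with linkage faster than 25% by month 3 and essentially no attrition.

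Third, the retention plan reports prior retention above 80%, a plausible basis for the 20%. The projected losses are survey-visit figures that the plan calls conservative, and follow-up before dropout still counts, so 67 per arm with no contribution from the rest is pessimistic. This is fair. Still, the primary outcome is self-reported at those visits, so the plan should say which figure it used.

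**Conclusion.** The concern holds. At the hazard ratio implied by 25% to 35%, ~80% power for texting only versus TAU is unattainable with 84 per arm at any time point. At the protocol's visit times it is about 30–62% with no loss and 25–53% at 67 per arm. The plan's OR proxy widens this to 41–78% and 34–68%, still short of 80%.

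For texting plus PRC versus TAU the position is mixed. Twelve-month rates give 80%, falling to 71% at 67 per arm; 6-month rates, or the OR of 2.45 as HR, leave it at 87–89% at 67 per arm. Whether ~80% survives attrition for that contrast depends on inputs the plan does not state.

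These results assume proportional hazards, constant hazards when extending rates to month 12, pairwise log-rank tests at two-sided 0.05, and, for the 67-per-arm figures, no follow-up from the 20% lost. The stated power needs correcting before it is relied on.

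**What to change.** Keep N=252 and replace the single figure in Cohort with power per contrast, for example: *Assuming [named event] in 25%, 35% and 45% by month [T], 84 per arm and two-sided 0.05, power is [x]% for arm-1 vs TAU (HR [ ], [ ] events) and [y]% for arm-2 vs TAU (HR [ ], [ ] events); with [z]% attrition, [ ]% and [ ]%.* Give the software inputs.

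In the same edit:
- Name the event. The rates quoted are for completed referrals, while the primary outcome is time to a first buprenorphine prescription.
- Make the OR range agree with the stated proportions, or state hazard ratios instead.
- Say which attrition figure was used and how it entered, and reconcile the 20% with Subject Payment and Projected attrition rates.
- If ~80% was meant for another test, such as a three-arm trend test, name it and still report the pairwise powers.
- Under Proposed Analyses, state that texting only versus TAU is underpowered and will be read mainly through its estimate and confidence interval. Say the same for arm-1 versus arm-2, which the plan does not claim to power but the ordered hypothesis involves (27%, 40% or 51% with no loss for 12-, 6- or 3-month rates).

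The cost is rewording of the two sample-size paragraphs and one interpretation sentence, with no extra participants. The stated power becomes less favourable.
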